#### 7.6.1.2 Community sensitization

Prior to ATSB deployment, community sensitization activities will be conducted to prepare communities for intervention and research activities. Community sensitization begins with the County and sub-County Health Management teams and the Division of National Malaria Program.

Community sensitization activities will be informed by initial qualitative research activities undertaken to understand community member knowledge and perceptions regarding ATSBs based

on experiences from the validation studies. Community sensitization meetings (which may include ‘barazas’) will be held in all intervention area communities. All community members will be invited to the meetings, and monitoring assistants and study staff, together with community leaders (e.g. elders, school teachers, religious leaders), will provide an overview of the ATSBs and instructions, as noted above. The community leaders and monitoring assistants, study staff, and community leaders will be trained about the ATSBs and will answer community member questions and address concerns. If they are unable to address specific questions or concerns, the monitoring assistants will refer these questions to the field coordinator. Where appropriate, local media may be used to disseminate messages to sensitize the community to the intervention and the research. This may include posters, pamphlets, or other printed materials. At each ATSB monitoring visit, and at the time of ATSB removal and replacement, household members will have the opportunity to ask questions and voice concerns to the ATSB monitors who will respond, capture this information, and report any questions that they are unable to respond to to the field supervisor who will then work to respond to the household.

Sensitization meetings will also be held in control clusters to explain the trial and encourage appropriate care-seeking behaviour and usage of malaria prevention methods, including LLINs.

#### 7.6.1.3 *Monitoring of ATSBs*

At the first visit during month 0, new ATSBs will be installed. At month 7, month 13, and month 19 (every six months), all installed ATSBs will be replaced with new ATSBs. Full coverage of fully functional ATSBs will be maintained for the duration of the study. Community-based monitoring assistants will be trained and will be responsible for visiting intervention households monthly throughout the trial. Additionally, household heads in intervention areas will be instructed to contact monitoring assistants for a replacement bait station if one is damaged or missing in between monitoring visits.

The monitoring assistants will be equipped with a supply of ATSBs and necessary materials for installing, replacing or re-hanging damaged or missing devices. During each monthly visit, the monitoring assistants will ensure eligible structures in study areas are covered with correctly installed ATSBs according to the manufacturer instructions. They will replace damaged or missing ATSBs as needed and record information about the ATSB condition in electronic data capture forms on a smartphone or tablet. The monitoring assistants will attempt to recover any missing ATSBs for proper disposal. They will respond to and record questions or concerns voiced by the household members to the field supervisor. At the end of their sixth month period, or if they are damaged or missing, they will be collected and incinerated in a high-temperature incinerator, per manufacturers instruction (see Section 16.3, Annex III: ATSB Stations: Disposal options assessment, page 80).

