### 3.3 ATSBs

Westham Co., based in Israel, recently developed a bait station containing a fruit syrup to attract mosquitoes, sugar to stimulate feeding, and an active ingredient (the neonicotinoid, dinotefuran) to kill the foraging vectors. The bait station contains a commonly used bittering agent called Bitrex (<https://www.bitrex.com/en-us>) that deters human and animal consumption of the bait. The bait stations also contain a pH regulator (citric acid), preservative (sodium benzoate), and thickener (xanthan gum). They have a protective membrane that covers and protects the bait from rain and dust but allows mosquitoes to feed through it (See Figure 1: ATSB station, page 12). The protective membrane will enable mosquitoes to feed, but it serves as a barrier to non-target organisms. Field studies to-date have also shown that the ATSB has a minimal impact on non-target organisms (NTOs) and humans. This includes evidence specifically for the toxicant that will be used, dinotefuran [12]. The Westham ATSB can remain effective in the field for at least six months and has a shelf life greater than three years with no specific storage requirements. This ATSB is now being produced at an industrial scale, uses simple and widely available ingredients, and limits environmental contamination with insecticides.

ATSBs may be an essential vector control tool in the context of insecticide resistance. Insecticide resistance for the six insecticide classes currently used in LLINs and IRS threatens malaria prevention efforts. Resistance to pyrethroids (used in LLINs and IRS) is commonly reported (<http://www.irmapper.com>). If pyrethroids lose most of their efficacy, more than 55% of vector control benefits could be lost [13]. ATSBs can help mitigate insecticide resistance to these contact insecticides because they can use ingestion toxicants from very different chemical classes. Many existing ingestion toxicants may be used in a bait station, facilitating resistance management strategies, such as rotation or combination approaches.

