#### 6.3.7.2 *Continuous monitoring and maintenance of ATSBs*

A monitoring component will ensure that ATSB coverage remains high for the duration of the study. Community-based monitoring assistants will monitor all or a sample of bait stations about once per month and capture data on placement and condition. The bait stations will be replaced as required or every six months (the product's lifespan). Continuous monitoring will also include participant education, routine communication to ensure proper ATSB deployment and use, and the opportunity for household members to ask any questions or voice any concerns.

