### 7.7.1 Cluster-level adherence

In intervention clusters, adherence at the cluster level will be defined as a cluster where ATSBs were deployed and replaced according to the planned schedule. Non-adherence in intervention clusters will be defined as clusters where there was more than one-month delay in ATSB deployment during a two year period.

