#### 9.1.5.4 Bait station durability

1. To examine the durability of the bait stations during the first 6-month deployment, a selection of ATSBs will be randomly sampled from households within ATSB study clusters. Stations collected from households will be immediately replaced with new stations.
2. The bait station will be placed in a 30cm x 30cm x 30cm cage and 100 female *An. gambiae* or *An. arabiensis* (collected as larvae and reared in the lab) will be introduced into the cages after an appropriate period of starvation.
3. Mortality will be recorded at 24 hours.
4. The number of dead and live mosquitoes will be recorded at 48 hours.

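### The listed bait-station months (0, 7, 13, 19) do not give the stated six-month interval, and per-protocol adherence is judged against that schedule

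*Protocol*

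**What the plan says.** Section 7.6.1.3 sets the operative schedule. Installation: "At the first visit during month 0, new ATSBs will be installed". Replacement: "At month 7, month 13, and month 19 (every six months), all installed ATSBs will be replaced with new ATSBs". Disposal, later in the same section: "At the end of their sixth month period, or if they are damaged or missing, they will be collected and incinerated". The section also commits the trial to complete coverage with working stations throughout, supported by monthly visits at which damaged or missing stations are replaced.

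Other sections give six months without listing months. Section 6.3.7.2 says "The bait stations will be replaced as required or every six months" and describes that period as the life of the product. The technical summary (2.4.1), the environmental risk section (11.3.2) and the section on protection against insecticide exposure (11.3.3.1) agree. The background is slightly more generous: "The Westham ATSB can remain effective in the field for at least six months" (section 3.3).

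Section 7.7.1 calls an intervention cluster adherent if stations were deployed and replaced on the planned schedule. Non-adherent clusters are "clusters where there was more than one-month delay in ATSB deployment during a two year period". Section 9.4.2.1.2 excludes non-adherent clusters from the per-protocol population. The durability study in 9.1.5.4 is framed as follows: "To examine the durability of the bait stations during the first 6-month deployment".

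**The concern.** A site cannot carry out section 7.6.1.3 as labelled. From a month-0 start, replacement at month 7 is not six-monthly, and each literal way through breaks another commitment:

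- Stations stay up until month 7. First-round stations still in place then pass both the stated product life and the end-of-sixth-month collection rule.
- Stations are collected at the end of month six and replaced at month 7. Structures then go about a month without stations, against the full-coverage commitment.

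The schedule also feeds the analysis. If the planned date of the first replacement can be read two ways, so can the one-month delay rule and therefore membership of the per-protocol population. If clusters have been replaced on different readings, they can later be classified only by a judgement made after the fact.

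**Working it through.** **Inputs.** Installation at month 0 and replacement at months 7, 13 and 19 (7.6.1.3); a two-year deployment, taken as 24 months (2.4.1); a stated interval of six months (7.6.1.3, 2.4.1, 6.3.7.2, 11.3.3.1); a tolerance of one month (7.7.1); a design effect of a 30% reduction (7.8.1.1).

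**Intervals as listed.** 7 − 0 = 7; 13 − 7 = 6; 19 − 13 = 6; 24 − 19 = 5; total 24. The stated interval is reproduced for the second and third rounds but not for the first.

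**What would reproduce it.** A six-month cycle from month 0 gives 0, 6, 12, 18. A six-month cycle from month 1 gives 1, 7, 13, 19. The protocol combines the start of one with the replacement months of the other. If the labels are treated as one-month windows, the first round lasts between 7 − 1 = 6 and 8 − 0 = 8 months, and the gap from month 7 to month 13 lasts between 13 − 8 = 5 and 14 − 7 = 7. The window reading therefore allows six months but does not fix it.

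**Effect on adherence in the first round.** Delay = actual month − planned month; the cluster is non-adherent if delay exceeds 1.

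| Actual replacement | Planned at month 7 (as listed) | Planned six months after month 0 |
|---|---|---|
| Month 7 | 0, adherent | 1, adherent |
| Month 8 | 1, adherent | 2, non-adherent |

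The two readings classify a cluster differently when its first replacement falls after month 7 and no later than month 8.

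**Upper bound on dilution.** Assume that the listed months are followed literally, that the intervention has no effect in the seventh month, and that events accrue evenly. The affected share is 1/24 = 4.2% of intervention time, and the reduction becomes 0.30 × 23/24 = 28.75% over two years. On the same assumptions at one year it is 0.30 × 11/12 = 27.5%. Section 7.8.1.1 states 90% power for a 30% reduction and 80% for a 26% reduction, so even at this bound the planned power over two years lies between 80% and 90%.

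**The case against.** The strongest reply is that this is a labelling slip. Apart from the listed months, the protocol consistently says six, including the timeline in Table 8, and months 7, 13 and 19 are exactly six apart. Installation during month 0 can be read as a roll-out window, followed by six full months of use and replacement as month 7 opens, which fits the collection rule. That may well be the intention. It does not dispose of the point, because the text never says so, and the listed months are the only explicit calendar from which a site or an analyst can read the schedule.

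A second reply is that section 7.7 leaves adherence measures to be defined before the final analysis, and that 9.4.2.1.2 allows monitoring data to refine the per-protocol population in the SAP. The primary analysis is by intention to treat. All of this is correct, and it limits the consequence to secondary analyses. However, 7.7.1 already fixes a one-month rule, and the schedule it refers to is the one that is unclear.

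A reader might also infer that every first-round station in all 40 intervention clusters will hang past its useful life and that this will materially dilute the effect. The documents do not support that. Damaged or missing stations are replaced earlier. Section 3.3 gives six months as a minimum, and Annex III (section 1.2) expects dinotefuran content at six months to be close to the starting level. Annex III also bases the interval on the life of the station rather than on loss of insecticide, so it does not show that a seven-month-old station works. Loss of effect is therefore neither shown nor excluded.

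**Conclusion.** The contradiction is real and sits within section 7.6.1.3: the listed months, the six-month label and the sixth-month collection rule cannot all hold from a month-0 start. It affects the first round as listed and, through 7.7.1 and 9.4.2.1.2, the definition of the per-protocol population.

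The numerical stake for efficacy is small: at most 1.25 percentage points off a 30% reduction over two years (30 − 28.75), and only under the no-effect assumption and a literal reading of the months. A reader might likewise conclude that per-protocol clusters will hold eight-month-old stations. That age arises only if the one-month tolerance is added to the literal month 7; on a six-month interval the same tolerance gives seven months. The point rests on a schedule that cannot be executed as written and on an uncertain reference for adherence, not on lost power.

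**What to change.** Reconcile the listed months in 7.6.1.3 with the six-month interval and the end-of-sixth-month collection rule, so that they describe one schedule consistent with 2.4.1, 6.3.7.2, 11.3.2 and 11.3.3.1. Which schedule that is remains for the sponsor to decide. State in 7.7.1 the reference date from which the one-month delay is measured, for example a fixed calendar month or the cluster's own preceding installation.

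Only if the reconciled schedule, with its tolerance, allows stations older than six months should the durability sampling in 9.1.5.4 reach that age. As it stands, that sampling covers the first six-month deployment, and the review in 10.4.2.6 flags only durability shorter than six months.

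The cost is a wording change in two sections, ideally before deployment, plus a few older durability samples if that condition applies. The sample size and the primary analysis are unaffected.

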#### 7.6.2 **Control cluster interventions**

Between March and June 2021, the Government of Kenya is planning a mass LLIN distribution campaign throughout Siaya County (the study area is within Siaya County). Through our baseline continuous household survey (cMIS), we will evaluate LLIN coverage in all intervention and control clusters. Based on the findings, we may plan a “top-up” distribution to ensure equal coverage across arms.

#### 7.6.3 **Other malaria control interventions**

Community-case management of malaria by community health volunteers is an active intervention promoted by the Ministry of Health in this area. In this strategy, community health volunteers test and treat participants encountered in the households who complain of symptoms compatible with

malaria. Additionally, in September 2019, the Kenya Ministry of Health began a phased implementation of GSK's Mosquirix vaccine in children aged 5-17 months of age. Rarieda sub-county was chosen as an initial vaccinating sub-County, whereas Alego-Usonga was not. To control for the impact of RTS,S/AS01 on our study outcomes, we will ensure a balance of clusters between arms in Rarieda and Alego-Usonga sub-Counties. Additionally, we will record the vaccination status of all children <5 years of age from the maternal-child booklet or from vaccination cards. Where available, we will take a photograph of the child's vaccination records. Where not available, we will use maternal recall. The Kenya Division of National Malaria Program (DNMP) does not currently have plans to perform IRS in Siaya County during the trial period. Should IRS be implemented in the trial area during the trial, the study team will monitor timing and coverage of the campaign at a household and cluster level but will not be responsible for regulating or "topping up" IRS should DNMP initiate spraying in the area.

## 7.7 ADHERENCE AND PROTOCOL DEVIATIONS

Both individual and cluster level adherence measures will be defined and pre-categorized prior to final analysis and used to categorize the per-protocol trial population. Since the intervention is deployed on a group basis rather than individually, adherence definitions will take account of this.

### 7.7.1 Cluster-level adherence

In intervention clusters, adherence at the cluster level will be defined as a cluster where ATSBs were deployed and replaced according to the planned schedule. Non-adherence in intervention clusters will be defined as clusters where there was more than one-month delay in ATSB deployment during a two year period.

### 7.7.2 Household-level adherence

Household-level adherence will be evaluated in the intervention cluster arms through ATSB monitoring visits. For each household, "expected ATSB-time" will be calculated by multiplying the total number of expected ATSBs hanging (2-3 ATSBs per structure) by the duration of time between visits (approximately four weeks). "Actual ATSB-time" will be calculated by multiplying the observed number of ATSBs during the monitoring visit by the duration of time they were hanging. The ratio of "actual ATSB-time" over "expected ATSB-time" will be expressed as a percentage and used as the measure to evaluate household-level adherence. For example, if a household has ten structures, and the intention is to have two ATSBs per structure, there should be 80 ATSB-weeks over four weeks (10x2x4). If the household had only one ATSB hanging on each structure between visits, the household would have an observed ATSB-time of 40 ATSB-weeks (10x1x4) and a household adherence of 50% (40/80).

### 7.7.3 Individual-level adherence to antimalarial treatment among cohort members

A random subset of cohort participants who have recently been treated for malaria may be re-visited within one week to assess adherence to the study medication. At this time, study staff will ask questions about the total number of doses taken and request to view the blister pack that contained the treatments that the participant took.

### 7.7.4 Protocol deviations

Protocol deviations will be considered as the cluster and individual level using the above-described definitions for adherence. Protocol deviations related to failure to carry out other study procedures such as outcome assessment on a standardized schedule will not be considered reportable to DSMB unless they affect an entire cluster and delay primary outcome assessment by more than two

months. Protocol deviations related to failure to deliver or replace ATSB will be summarized in the final trial reports and incorporated into the calculation of adherence.

## 7.8 SAMPLE SIZE

The number of study clusters identified for this study was driven by sample size considerations for the primary endpoint, malaria case incidence.

### 7.8.1 Malaria case incidence cohort

#### 7.8.1.1 *Main trial*

The sample size was calculated using the 'Tests for the Difference Between Two Poisson Rates in a Cluster Randomized Design' module in PASS 2020 (©NCSS, Kaysville, Utah). The observed event rate in this age group was 1,128 per 1000 person-years in the control arm of a recently completed mass test-and-treat trial in this area. A more conservative event rate of 845/1000 will be used, which is 25% lower than the previously observed event rate of 1,128/1000 person-years. This is done to account for an estimated 7.4% overall reduction in event rates in children 1-<15 years due to the implementation of the RTS,S/AS01E vaccine (vaccine efficacy 39.0%) in two-third of the study area in children 1-<5 years of age (28.6% of the sample study cohort) ( $0.39 \times 0.67 \times 0.286 = 0.074$ ), plus a further 17.6% reduction in malaria due to unforeseen changes in environmental factors, or boosting of other malaria control measures such as the scaling up of integrated community-based case management. The coefficient of variation in this previous study was 0.4.

A total sample size of 2,240 person-years (1,120 per arm, or 28 person-years per cluster) is required to detect a  $\geq 30\%$  reduction in the incidence of clinical malaria among children aged 1-<15 years (the primary outcome) from 845 per 1000 person-years in the control arm to 592 in the intervention arm over two years, allowing for 20% loss of person-time due to LTFU, or exclusion of person time after a clinical event treated with artemether-lumefantrine during a six month follow-up period resulting in 1,760 person-years completed (22 person-years per cluster, 880 person-years per arm) (80 clusters [40 per arm], CV=0.4 in both arms, two-sided  $\alpha=0.049$ , power=90%). No sample size inflation is required two allow for two interim analyses because a similar sample size is needed (2,240) for a study with a final two-sided  $\alpha$  of 0.049 as for a study with a single analysis using a two-sided  $\alpha$  of 0.05.

The intention is to follow each child for 6.5 months. This includes two weeks of lead-in time that do not contribute to the analysis. These are the first two weeks after the initial presumptive treatment with artemether-lumefantrine to clear any existing parasitaemia. This will then be followed by six months of follow-up time that contribute to the analysis. We will use a more conservative average follow-up time of five months per participant to allow staggered enrolment of participants over time. This means that not all children towards the end of the 2-year trial will complete the full 6.5 months. The 2,240 person-years will thus be obtained by sampling approximately 67.2 individuals for an average of five months each in 80 clusters ( $67.2 \times [5/12] \times 80 = 2,240$ ).

The same sample size will also have 80% power to detect a 26% reduction from 845 to 622 per 1000 person-years with all other parameters kept the same, or 80% power to detect a 30% reduction if the CV was 0.488 instead of 0.4. Similarly, the study would have at least 80.0% power to detect a significant difference at the first interim analysis when 50% of the events have occurred in the control arm if the effect size is 41.2% instead of 30% ( $\alpha=0.001$ , using Haybittle-Peto type boundaries, see 9.4.1, Interim analysis, page 44).

#### 7.8.1.2 *Baseline cohort*

The baseline cohort will be conducted during a period of approximately six months in 100 (instead of 80) potential clusters before the deployment of ATSB. The sample size for the baseline cohort will be 550 per year, obtained by following 11 participants per cluster for an average of five months each ( $11 \times [5/12] \times 100$ ). The sample size is based on similar sample size considerations per cluster as for the main trial but adjusted to a six month instead of a 2-year period. The average of five months each (with a maximum follow-up time of 6.5 months per participant) is used to take a staggered enrolment into the cohort into account (i.e., not all participants will have contributed the full 6.5 months before the start of the main trial).

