### 2.4.2 Lay Summary

Increasing insecticide resistance and changes in the malaria-transmitting mosquitoes' behaviour toward early evening and outdoor biting threatens the effectiveness of the current tools to reduce the malaria-transmitting mosquito. A new tool, the Attractive Targeted Sugar Bait (ATSB), is designed to attract and kill mosquitoes using a sugar attractant laced with insecticide, including those that escape the killing effect of conventional tools, such as indoor spraying with insecticide and insecticide-treated bednets. It reduces the lifespan and density of the malaria-transmitting mosquito population and can reduce malaria transmission when deployed at scale. We will conduct a large trial involving about 80 village-clusters. During a 2-year period, in half of these villages, households will receive two or three ATSB 'bait stations' per household structure every six months to hang outside on their exterior walls. The study aims to reduce the burden of malaria by reducing the number of malaria-infected mosquitoes in the area. This will be assessed by comparing the number of clinical episodes of malaria among 5,376 children aged 1-15 years in the intervention and control villages. The children will be visited at home every month for six months each. The study also includes nested studies assessing the impact ATSBs on mosquito densities and behaviour, acceptability and feasibility studies of ATSB deployment, and assessing the cost-effectiveness of the intervention. The study will take about three years, including about six months to collect baseline data before the ATSBs are used, two years of intervention and six months for data analysis and reporting. Similar studies will be conducted in Zambia and Mali.

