### 6.3.2 Baseline data collection

The baseline malaria incidence, prevalence, and contextual data will be collected in a cohort study (6.3.3.1, below) and household survey (6.3.3.3, below) conducted in 100 clusters prior to ATSB deployment. This data will be used to inform the restricted randomization and select the 80 clusters for inclusion in the main trial. The incidence and prevalence data will also be used to confirm the necessary sample size for the cohort and household survey required for the main trial to assess impact. Baseline entomological data (including mosquito age structure, mosquito density, sporozoite rates, insecticide resistance, and EIR) will be collected in 30 randomly selected clusters to inform the restricted randomization.

[figure not shown]

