## 7.4 WITHDRAWAL/FOLLOW-UP

Based on prior cohort studies in the area, we anticipate an approximate 20% refusal, LTFU, or withdrawal from each cohort. This is accounted for in the sample size calculations. The level of non-participation in household surveys is expected to be less than 20%.

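### The baseline cohort's printed formula gives 458 person-years, not the stated 550, and the registration table's 2,400 person-years contradicts the main trial's derived 2,240

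*Protocol*

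**What the plan says.** **Baseline cohort.** Section 7.8.1.2 states the planned size as follows: "baseline cohort will be 550 per year, obtained by following 11 participants per cluster for an average of five months each". The formula printed after it is 11 x [5/12] x 100. On duration it says: "The baseline cohort will be conducted during a period of approximately six months in 100 (instead of 80) potential clusters". On the basis of the size it says: "The sample size is based on similar sample size considerations per cluster as for the main trial but adjusted to a six month", in place of two years. It explains the five-month average by staggered enrolment within a maximum of 6.5 months per child.

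**Baseline duration elsewhere.** The Lay Summary (2.4.2) describes a study of about three years, "including about six months to collect baseline data before the ATSBs are used". Section 6.1 instead refers to a baseline year in which the 100 clusters are followed for one year.

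**Main cohort.** Section 7.8.1.1 requires 2,240 person-years (1,120 per arm, 28 per cluster) and allows for 20% loss of person-time, "resulting in 1,760 person-years completed (22 person-years per cluster, 880 person-years per arm". It then says: "The 2,240 person-years will thus be obtained by sampling approximately 67.2 individuals for an average of five months each in 80 clusters". The Technical summary (2.4.1) repeats 2,240, with 5,376 participants. The target sample size row of the trial registration table gives 2,400 person-years and 1,200 per arm.

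**Use of the baseline data.** Section 6.3.2 says: "The incidence and prevalence data will also be used to confirm the necessary sample size for the cohort and household survey". Section 8.1 (Table 3) lists baseline cohort incidence among the factors for the restricted randomisation.

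**The concern.** A stated total that is not the product of its own formula leaves the planned size of the baseline cohort undefined. One reader would plan for 458 person-years and another for 550. The unit adds to the doubt: a size per year is an odd description of a cohort lasting about six months, and the protocol gives two baseline durations.

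The registration table is a separate matter. Registration data are what outside readers see, and this entry disagrees with the sample-size section on the main cohort.

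The stake is a correct statement of how much information the baseline cohort will provide for choosing and balancing clusters and for confirming the main sample size. The main trial's operating characteristics are not at stake.

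**Working it through.** **1. The main-trial formula, as a check on the method** (Section 7.8.1.1: 67.2 children per cluster, five months, 80 clusters)

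- 67.2 x 5/12 x 80 = 2,240, as stated.
- 28 x 80 = 2,240.
- 67.2 x 80 = 5,376 children, and 5,376 x 5/12 = 2,240, as in the Technical summary.

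The method reproduces exactly. This 2,240 is a figure before loss; the figure after loss is 1,760.

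**2. The baseline formula** (Section 7.8.1.2: 11 children per cluster, five months, 100 clusters)

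- 11 x 5/12 x 100 = 458.3 person-years, against 550 stated.
- Shortfall: 550 - 458.3 = 91.7 person-years; 91.7/550 = 16.7%.
- Children: 11 x 100 = 1,100.

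**3. What would give 550**

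| Change | Arithmetic |
|---|---|
| Six-month average, 11 per cluster | 11 x 6/12 x 100 = 550 |
| Five-month average, more children | 550/100 x 12/5 = 13.2 per cluster (1,320 children, 220 more) |
| A quarter of the main trial's completed person-years per cluster | 22/4 x 100 = 550 |

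The 6.5-month maximum gives 11 x 6.5/12 x 100 = 595.8, so it does not explain 550. A literal annual rate does not either: 458.3 person-years in six months would be about 917 per year.

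**4. How much the difference means per cluster** (rates of 845 and 1,128 per 1000 from Section 7.8.1.1)

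- At 4.58 person-years: 4.58 x 0.845 = 3.9 to 4.58 x 1.128 = 5.2 expected events.
- At 5.5 person-years: 5.5 x 0.845 = 4.6 to 5.5 x 1.128 = 6.2 expected events.

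Assuming Poisson counts within a cluster, the relative standard error of one cluster's rate at the lower incidence is 1/sqrt(3.87) = 51% against 1/sqrt(4.65) = 46%. Either way a single cluster's estimate is imprecise.

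**5. The registration table**

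- 2,400 - 2,240 = 160 person-years; 160/2,240 = 7.1%.
- At five months, 2,400 would need 2,400 x 12/5 = 5,760 children, or 72 per cluster. Neither number appears in the protocol.

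**6. Main-trial power** (22 completed person-years per cluster, 40 clusters per arm, CV 0.4, rates 0.845 and 0.592, two-sided alpha 0.049; normal approximation for cluster Poisson rates)

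- Variance of the rate difference: [(0.845 + 0.592)/22 + 0.4² x (0.845² + 0.592²)]/40 = 0.00589; standard error 0.0768.
- 0.253/0.0768 = 3.30; less 1.97 gives 1.33, hence power of 90.8%.

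The stated 90% holds on the figures in Section 7.8.1.1 and uses neither 550 nor 2,400.

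**The case against.** The strongest reply is that both points are editorial. The baseline cohort has no power target. The instruction of 11 children per cluster is clear to field staff. The incidence tolerance for the restricted randomisation is left until data are available, so nothing is computed from the printed total. All of this stands and sets the severity.

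On duration, the one-year baseline in Section 6.1 may cover the household survey, which Section 7.8.2.2 sizes for a baseline year, with only the cohort lasting about six months. That is plausible, but Section 6.1 does not say so and the Lay Summary gives about six months for baseline data generally. On the unit, per year is probably a slip for person-years; that still needs correcting and does not change the product.

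Three stronger readings are tempting, and the protocol does not support them:

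- *The total is the error and 458 was intended.* The five-month average is stated twice and explained, which favours 458. But 550 is exactly what 11 children at six months give, and exactly a quarter of the main trial's completed person-years per cluster. The text does not decide between them.
- *The baseline cohort is too small by the main trial's standard.* A quarter of 28 is 7.0 person-years per cluster, against 4.58. But Section 7.8.1.2 claims only similar considerations, not the same ones, and sets no precision target.
- *A further 20% must come off.* Section 7.4 says "we anticipate an approximate 20% refusal, LTFU, or withdrawal from each cohort. This is accounted for in the sample size calculations", but that 20% includes refusals, who contribute no follow-up to begin with, whereas the 20% in Section 7.8.1.1 is lost person-time. A net baseline figure from either would be a scenario, not an error in the document. Nor is there support for treating the five-month average as already net of loss, since the main trial uses the same five-month formula for its figure before loss.

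**Conclusion.** The point holds, at minor severity. The stated baseline size and its printed derivation disagree by 17% (550 against 458 person-years). The document does not show whether the total, the number per cluster or the average follow-up is wrong. The unit is wrong for a cohort of about six months, and the baseline duration is not stated consistently. The registration table overstates the main cohort by 160 person-years (7%). There the direction is clear, because 2,240 is derived in Section 7.8.1.1 and repeated in the Technical summary.

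A reader might infer that the trial is underpowered or its primary analysis compromised. Neither follows: the 90% power reproduces from the figures in Section 7.8.1.1, and the unadjusted primary analysis does not use the baseline cohort. What is affected is the stated information behind baseline incidence, which informs the restricted randomisation, the selection of 80 clusters from 100 and the confirmation of the main sample size. The conclusion rests only on the protocol's own numbers, reading the baseline size as person-years.

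**What to change.** 1. In Section 7.8.1.2, make the total, the number per cluster and the average follow-up agree. If 11 per cluster and five months stand, restate the size as about 458 person-years from 1,100 children and, following the main trial's convention, describe it as a figure before loss. If 550 is the target, change either the number per cluster (13.2 at five months) or the average follow-up (six months with 11) and justify it.
2. Correct the unit from per year, presumably to person-years.
3. Reconcile the six-month baseline cohort (Section 7.8.1.2, Lay Summary) with the one-year baseline in Section 6.1, for example by stating which activity lasts how long.
4. In the registration table, change 2,400 person-years (1,200 per arm) to 2,240 (1,120 per arm).

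The cost is wording only, unless the sponsor confirms 550 at a five-month average. In that case enrolment rises by 220 children, from 1,100 to 1,320.
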